1. RESEARCH DESIGN

This will be a cluster-randomized comparative effectiveness trial conducted of patients with a primary care provider (PCP) diagnosis of COPD and/or asthma seen in outpatient primary care provider clinics (i.e. Family Medicine, Miles Square Health Center, and Academic Internal Medicine) as well as the CRC (Clinical Research Center) at the University of Illinois Hospital and General Internal Medicine and Family Medicine Clinics

at Cook County Health and Hospitals Systems (CCHHS). Providers will be randomized and their patients who fulfill the inclusion criteria will receive the intervention or be in the usual care group. Adults with a clinician-diagnosed COPD and/or asthma at high risk for diagnostic error due to lack of spirometry will undergo the REDEFINE intervention or usual care based on the PCP randomization. Outcomes will be assessed every 3 months for up to one year.

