2. If the spirometry findings are normal, with approval from the PCP, will de-escalate respiratory medication therapy via a stepwise process and schedule patient back for a repeat pre and post bronchodilator spirometry within 1-2 weeks at the same time and place as the PCP clinic session. Again with the PCP approval, this deescalation and repeat spirometry can occur in 1-2 week intervals until all maintenance medications are discontinued as long as the pre and post spirometry continues to be normal. After each visit, the following will be provided to the provider and patient: a letter summarizing the interpretation of the findings using GOLD/GINA criteria with recommendations for initial guideline driven therapy based on GOLD/GINA guidelines, if appropriate. Subjects will be managed by their PCP thereafter.
3. All spirometry test results and the subject's assessment at the time of the test will be uploaded into the subject's electronic health record for future reference.

D) Outcome Measures:

1. Primary outcome:

- (i) Accurate classification of patient as having COPD and/or asthma
- (ii) All-cause and respiratory related, acute care outpatient visits, ED visits, and hospitalizations

2. Secondary outcome:

- (i) Appropriate use of respiratory medications based on guidelines
- (ii) Use of other diagnostic testing: ECG, echocardiograms, CT/CXR, stress testing, cardiac catheterization, other pulmonary function tests
- (iii) Initiation of guideline based therapy
- (iv) Quality of life measures

E) Data collection and follow-up

1) Baseline data collection obtained at visit zero (V_0), in addition to those listed under intervention and usual care:

- 1. Demographic data (gender, age, self-reported race)
- 2. SES related measures: median household income
- 3. Level of education
- 4. Type of health insurance or self-pay
- 5. Up to two emergency contacts information
- 6. List of current respiratory medications from subject's pharmacy and verification with patient
- 7. Co-morbidities
- 8. History of prior ED visits or hospitalizations in the past one year with associated cause
- 9. EQ-5D 5L +B Bolt-on
- 10. SF-36 short form
- 11. Social support survey

2) All subjects will have their medical charts reviewed every 3 months after the initial visit (MR_1 , MR_2 , MR_3 , MR_4) up to one year. These electronic medical chart reviews will be used to obtain follow-up data since last study contact.

- 1. Change in type of health insurance or self-pay

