- 2. List of current respiratory medications from subject's pharmacy and verification with patient
- 3. Use of diagnostic testing: ECG, echocardiograms, CT/CXR, stress testing, cardiac catheterization, other pulmonary function tests
- 4. Any ED visits or hospitalizations or acute outpatient care visit and associated cause.
- 5. Healthcare utilization outside of U of I system (e.g. testing such as spirometry, ED and hospitalizations) if available through scanned records

3) All subjects will be contacted every 3 months after the initial visit via telephone (T_1 , T_2 , T_3 , T_4) up to one year; or they will be given the option to complete in person based on subject's convenience, for example they have a doctor appointment near time of study follow-up. These phone calls will be used to obtain follow-up data since last study contact. A reminder post-card will be mailed to the subjects a month before the next telephone contact.

- 1. Change in type of health insurance or self-pay

2. List of current respiratory medications from subject's pharmacy and verification with patient
3. Use of diagnostic testing: ECG, echocardiograms, CT/CXR, stress testing, cardiac catheterization, other pulmonary function tests
4. Any ED visits or hospitalizations or acute outpatient care visit and associated cause.
5. Healthcare utilization outside of U of I system (e.g. testing such as ancillary testing, ED and hospitalizations)
6. mMRC
7. A respiratory exacerbation history
8. EQ-5D 5L +B Bolt-on
9. SF-36 short form (at 3, 6 and 12 months)
10. Social support survey (at 6 months and 12 months)

F) Monetary compensation of subjects

1. PCP compensation:

UI Health and MSHC PCPs will receive \$95 in cash after completion of the education session. For CCHHS PCPs, the Division or Department will receive a total of \$95 per participant to be part of the divisional fund to be used by the PCP at their discretion as allowed by their institution.

2. Patient subject compensation:

Baseline visit (Vo):

Same for Intervention and usual care groups: Subjects will be provided \$75 in cash for completing the initial study visit.

Telephone contact (T₁-T₃):

Same for Intervention and usual care groups. Subjects who choose to complete the follow-up in person or via telephone will receive \$20 in cash at the time of the visit or at a later specified time that is convenient for the subject.

Final contact (T₄):

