5. STATISTICAL ANALYSES

All data will be stored in a secure, locked location. Data will be entered and managed through the Research Electronic Data Capture (REDCap). REDCap is a secure web-based application for building and managing online databases. REDCap is provided by

the CCTS Design Analysis Core. Data will be analyzed for clinical effectiveness using intention-to-treat principles.⁶⁹⁻⁷¹ For **Aim 1**, we will evaluate the misdiagnosis rates of the intervened and usual care groups separately at the first visit. Then compare rates between groups by using a generalized linear mixed model for binary outcome with two cluster levels, PCP and hospital, to account for the dependence within clusters. For the **Aim 2**, to investigate the impact of the misdiagnosis over time (4 time points: 0, 3, 6, 9, 12 months) on the quality of life and healthcare utilization, we will fit generalized linear mixed models with time, group, and their interaction as the main predictors. Two cluster levels, PCP and hospital, will be specified in the model to account for the dependence within clusters^{72,73} and an appropriate link function will be used for each outcome. Clinical important confounders will also be adjusted in the models. Before these analyses we will use descriptive statistics to describe the sample, and any assumption behind each statistical method will be examined during the analysis. A two-sided p-value less than 0.05 would be considered as statistical significance. All the analyses will be conducted by using SAS 9.2 (SAS Inst., Cary, NC).

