For **Aim 3: Costs**: The intervention costs for the study include the cost of the spirometry test, the time of the CHW/health promoter, and time of pulmonologist to provide periodic oversight of spirometry validity. In addition to estimating the costs associated with the intervention it will be important to measure the healthcare utilization for participants included in the study. It is possible that the intervention leads to use of other healthcare resources, particularly if the patient is determined to be free of respiratory disease. Therefore, we will measure both respiratory-related and overall healthcare costs. To measure these costs, we will determine overall healthcare utilization and apply unit costs to each of the events. Using chart reviews, we will examine healthcare utilization during the follow-up period. We will categorize healthcare utilization into either respiratory-related or all other healthcare use. We will apply standardized prices to each of the utilization components to estimate the overall and respiratory-related healthcare resource use during the study period. The standardize prices will be based on either the National Committee for Quality Assurance standardize price list for their relative resource use measure or Medicare reimbursement rates. For medications, we will rely on average wholesale price of medications to assign an average price to each of the COPD and asthma-related medications.

Cost-Effectiveness: The secondary outcome measures included in the study will be used to estimate the effectiveness to be used in the cost-utility analysis. We will use responses to the EQ5D to estimate patient utility and use that in calculation of quality-adjusted life-years (QALY). The area under the curve will be compared between the two groups and the difference will be the incremental effect used in the cost-utility analysis.

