Cost-utility analyses: We will evaluate the cost-utility of the intervention compared to usual care over the study period using recommended methods for cost-effectiveness analysis.⁷⁴ To compare the cost-effectiveness of the intervention to usual care, the findings are summarized into a ratio that provides the results in terms of the costs per unit of effect. We will calculate the difference in intervention costs and respiratory-related healthcare resource use between groups to determine the numerator of the ratio and the denominator will be the difference in QALYs in the cost-utility analysis. These incremental cost-effectiveness ratios (ICERs) will represent the cost per gain in QALYs for the intervention compared to standard care. As part of the cost-utility analysis we will evaluate the uncertainty associated with the ICERs. We will use bootstrapping

methods to generate confidence limits for the ICERs.^{75,76} We will display the results graphically on a cost-effectiveness plane and generate cost-effectiveness acceptability curves for the intervention compared to usual care.^{77,78} Cost-effectiveness acceptability curves display the probability of the intervention being cost-effective given various threshold values.⁷⁸ Thus decision-makers can identify a threshold value appropriate for their setting and determine the probability that the intervention will be cost-effective. We will also conduct sensitivity analyses that use the measure of overall healthcare utilization in calculation of the costs, as there may not be perfect specificity in identifying respiratory-related costs during the follow-up assessments and the intervention may lead to differences in non-respiratory costs.

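### Aim 3 takes the raw difference in EQ-5D area under the curve as the QALY gain, with no baseline EQ-5D adjustment; the ICER bootstrap also names no resampling unit in a provider-randomized trial

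*Combined protocol and SAP*

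**What the plan says.** Section 5 (Aim 3, Cost-Effectiveness) takes utilities from the EQ-5D and defines the effect in one sentence: "The area under the curve will be compared between the two groups and the difference will be the incremental effect". The cost-utility paragraph makes that QALY difference the denominator of the ICER. It then plans bootstrap "methods to generate confidence limits for the ICERs", a cost-effectiveness plane, and a step to "generate cost-effectiveness acceptability curves for the intervention compared to usual care". Neither paragraph names a covariate or a resampling unit.

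The baseline value is available. Section 4 E lists the instrument ("EQ-5D 5L +B Bolt-on") at the initial visit and again at the quarterly contacts: "All subjects will be contacted every 3 months after the initial visit via telephone".

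Adjustment and clustering are addressed elsewhere in Section 5. The Aim 2 text says "Clinical important confounders will also be adjusted in the models", without naming them, and "Two cluster levels, PCP and hospital, will be specified in the model to account for the dependence"; the Aim 1 model has the same two levels. Nothing says that these provisions extend to Aim 3 or that the QALY difference will come from the Aim 2 quality-of-life model.

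The unit of randomization is the PCP (Section 1): "Providers will be randomized and their patients who fulfill the inclusion criteria will receive the intervention". Section 3 expects about 500 patients and at most 80 PCPs.

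**The concern.** **Baseline adjustment (main point).** Baseline EQ-5D is one of the five points that make up each patient's area under the curve (AUC), and it is correlated with the other four. If one arm starts higher by chance, its AUC is higher without any treatment effect. A comparison of raw AUCs passes that gap into the ICER denominator, and from there into the limits, the plane and the acceptability curves on which the Aim 3 hypothesis will be judged. Regression on baseline removes the part of the error that baseline predicts.

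**Resampling unit (secondary).** The plan does not say that patients will be resampled; it leaves the unit open. If patients were resampled, the stated uncertainty for costs and net benefit would not match the unit of randomization and would be too small when the ICC is above zero.

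No Aim 1 or Aim 2 result is affected.

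**Working it through.** The plan gives no SD, ICC, QALY or cost figure, so there is nothing of its own to reproduce.

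**Inputs from the documents:** EQ-5D at 0, 3, 6, 9 and 12 months; about 500 patients; at most 80 PCPs, hence at least 500/80 = 6.25 patients per PCP on average.

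**Assumed:** 250 patients per arm, utility SD 0.2, between-visit correlation r, ICC p of the AUC, and the costs and thresholds below.

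**1. Variance of the AUC.** The trapezoid weights over one year are 1/8, 1/4, 1/4, 1/4, 1/8. With unit variance and constant r:

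- variance of AUC: v = 0.21875 + 0.78125r
- covariance of AUC with baseline: c = 0.125 + 0.875r
- variance after adjustment: v − c²

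| r | v | c | v − c² | SE ratio, unadjusted/adjusted |
|---|---|---|---|---|
| 0.4 | 0.531 | 0.475 | 0.306 | 1.32 |
| 0.5 | 0.609 | 0.563 | 0.293 | 1.44 |
| 0.6 | 0.688 | 0.650 | 0.265 | 1.61 |
| 0.7 | 0.766 | 0.738 | 0.222 | 1.86 |

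If correlation instead decays with time from 0.6, 0.7 or 0.8 between adjacent visits, the ratios are 1.23, 1.34 and 1.55.

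**2. With clustering** (80 equal PCPs, m = 6.25), two cases bracket the answer. The example is r = 0.6, p = 0.05, with SE = 0.2 × √(2/250) × √variance.

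- *PCP effects stable over time.* Unadjusted: v[1 + (m−1)p] = 0.6875 × 1.2625 = 0.868, SE 0.0167. Adjusted: v − c² + (m−1)pv(1−c)² = 0.265 + 0.022 = 0.287, SE 0.0096. Ratio 1.74.
- *PCP effects arising after baseline.* The PCP variance is q = pv/(1−p) = 0.0362. Unadjusted: v + mq = 0.914, SE 0.0171. Adjusted: v − c² + mq = 0.491, SE 0.0125. Ratio 1.36.

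Over p = 0.02 to 0.10 and r = 0.4 to 0.7 the ratio runs from 1.35 to 2.16 (stable) and from 1.16 to 1.64 (post-baseline).

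**3. Effect of a chance gap.** The SD of the baseline difference, ignoring clustering, is 0.2 × √(2/250) = 0.0179. Multiplied by c (0.475 to 0.738), a one-SD gap moves the QALY difference by 0.0085 to 0.0132.

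Illustration with an assumed $1,000 cost difference and 0.03 QALY gain (ICER $33,300), at r = 0.6 without clustering:

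- baseline gap of ±1 SD alone (0.0116 QALY): about $24,000 to $54,400
- full unadjusted error of ±1 SE (0.0148): $22,300 to $65,900
- error remaining after adjustment, ±1 SE (0.0092): $25,500 to $48,100

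**4. Resampling unit.** For costs or the unadjusted AUC, the design effect is 1 + (m−1)p, and coverage of nominal 95% limits that ignore PCPs is 2Φ(1.96/√DE) − 1. With 80 PCPs and p = 0.02, 0.05, 0.10, DE is 1.105, 1.2625, 1.525 and coverage is 93.8%, 91.9%, 88.8%.

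Simulated coverage of percentile limits at ICC 0.05, patient versus PCP resampling:

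| Quantity | 80 PCPs | 40 PCPs |
|---|---|---|
| Adjusted QALY difference, stable effects | 93.9% vs 94.2% | 92.3% vs 93.7% |
| Adjusted QALY difference, post-baseline effects | 86.6% vs 94.0% | 79.9% vs 93.5% |
| Skewed costs | 91.0% vs 93.8% | 86.2% vs 92.0% |
| Net benefit at $100,000/QALY, stable | 92.5% vs 93.7% | 89.3% vs 93.2% |
| Net benefit at $100,000/QALY, post-baseline | 88.9% vs 93.8% | 84.1% vs 93.6% |

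The simulation used 4,004 runs per cell (Monte Carlo SE about 0.4 points), 500 resamples, r = 0.6, equal-sized PCPs, gamma costs with mean 6,000 and SD 12,000 independent of QALYs, cost ICC equal to AUC ICC, and true differences of zero. At ICC 0.02 with 80 PCPs the choice of unit hardly matters for costs (93.1% vs 93.2%) or for the adjusted QALY difference with stable effects (93.5% vs 93.7%). Missing EQ-5D was not examined, and net benefit stood in for the ratio itself.

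**The case against.** The strongest reply is that nothing here is an error. Randomization makes the raw difference valid, and a bootstrap of it carries baseline variation into the limits, which come out wider rather than wrong. That is correct, and it is why the main point is a recommendation about efficiency rather than a claim of bias.

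Adjustment also does not make the ICER stable. In the illustration the range after adjustment is still $25,500 to $48,100. With post-baseline clustering (ICC 0.05, 80 PCPs, SE 0.0125) it is about $23,500 to $57,300. This stands as a caution, but the fair comparator is the full unadjusted range: $22,300 to $65,900 without clustering, and about $21,200 to $77,500 in the clustered case. Adjustment narrows both. The $1,000 and 0.03 QALY are invented, and a small denominator makes any ICER volatile.

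The plan also sets no cost-effectiveness threshold, so no stated conclusion can be shown to flip.

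On the bootstrap, the Aim 1 and Aim 2 models show that the team recognizes PCP clustering, and the lowest coverage figures need few PCPs, post-baseline effects and a sizeable ICC together. This is a good reason to rank the point second. The Aim 2 quality-of-life model does include month 0 and both cluster levels, and the cost-utility paragraph cites general methods. Neither fixes a covariate for the QALY difference or a unit for the resampling.

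**Conclusion.** The concern holds. Aim 3 states a specific estimator without baseline adjustment, while a more precise one is available from data already collected. The precision lost is material throughout the range examined: an SE ratio of 1.23 to 1.86 without clustering, and 1.16 to 2.16 with 80 PCPs and an ICC of 0.02 to 0.10. An ordinary one-SD baseline gap is worth about 0.009 to 0.013 QALY at utility SD 0.2. These sizes depend on assumed SDs, correlations and ICCs, but adjustment gained precision in every case examined.

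The missing resampling unit is a clarification. Its importance runs from negligible (ICC 0.02, 80 PCPs, for costs or stable PCP effects) to substantial (about 80% coverage for the adjusted QALY difference with 40 PCPs, ICC 0.05 and post-baseline effects). Both points should be settled in the plan before the Aim 3 analysis.

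**What to change.** **Main change.** State that the incremental QALY is the arm coefficient from a regression of AUC on arm, baseline EQ-5D and hospital, refitted in every bootstrap replicate.

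**Clarification.** State that the bootstrap resamples whole PCPs within arm, keeps each patient's cost and QALY paired, and uses the same resamples for the ICER limits, the plane and the acceptability curves. Stratify the resampling by hospital only if PCP randomization was stratified by hospital; Section 4 A states no stratification. The sensitivity analysis on overall costs can stay as it is.

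**Cost.** Plan wording and analysis code only. Baseline EQ-5D is already needed for the AUC, so using it as a covariate loses no further patients. In the simulation at ICC 0.05, PCP-based cost limits were about 10% wider with 80 PCPs and 21% wider with 40, and percentile limits still covered slightly under 95%.

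For QALYs at r = 0.6 and ICC 0.05, adjusted PCP-resampled limits had 0.64 (stable) or 0.82 (post-baseline) times the width of unadjusted patient-resampled limits with 80 PCPs, and 0.67 or 0.98 times with 40. At ICC 0.10 with 40 PCPs and post-baseline effects the factor was 1.25, so adjustment does not always offset the widening.

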6. SAFETY MONITORING AND ASSESSMENT

Risks of intervention study

Spirometry is a breathing test commonly utilized in the outpatient primary care setting. Risks and discomforts associated with spirometry are possible. The risks include shortness of breath and on rare occasion, the subject might experience dizziness, cough, or light-headedness. A medication that can open subjects' airways may be used during spirometry testing. This medication, albuterol, is in a class of medications (i.e. short acting beta agonist) that is often used to treat subjects suspected with COPD and/or asthma as part of usual care. Albuterol may sometimes cause tremors/shaking, nervousness, dizziness, difficulty sleeping, headache, irregular heartbeats, drying or irritation of mouth, sore throat, upset stomach, and coughing. These effects usually disappear within a short time and do not require treatment.

Data Safety Monitoring Plan

The PI will review monthly data reports reviewing recruitment, consent, intervention activities, adverse events, and follow-up. Although few, if any, intervention-related adverse events are anticipated in this study, the study population is at risk for poor outcomes, including life-threatening exacerbations and death not caused by the study itself. The PI will comply with prompt reporting of any adverse event to the IRB

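### The incremental QALY is a bare comparison of EQ-5D areas, with no model and no handling of missed contacts or deaths; a weighted sum of mixed-model means, with a patient level added, is a better estimator at little cost

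*Combined protocol and SAP*

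**What the plan says.** Section 4E collects the EQ-5D at baseline ("Baseline data collection obtained at visit zero") and again at follow-up. There, "All subjects will be contacted every 3 months after the initial visit via telephone", up to one year, with an in-person option. The follow-up list includes "8. EQ-5D 5L +B Bolt-on" without restricting it to certain contacts, whereas the SF-36 skips month 9. The EQ-5D therefore has five planned values per patient.

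In section 5, the Cost-Effectiveness paragraph of Aim 3 takes utilities from the EQ-5D and continues: "The area under the curve will be compared between the two groups and the difference will be the incremental effect". That difference is the denominator of the ICER. Bootstrap confidence limits are planned, but the resampling unit is not named. The sensitivity analyses change only the definition of cost.

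For Aim 2, the same section plans a model for quality of life at the same five months: "we will fit generalized linear mixed models with time, group, and their interaction as the main predictors". It names the primary care provider (PCP) and the hospital as levels. No patient effect or within-patient covariance is named, and Aim 3 does not refer to this model. Intention to treat is stated for clinical effectiveness, with no rule for a missing utility.

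Section 6 describes the population as at risk of poor outcomes, "including life-threatening exacerbations and death not caused by the study itself".

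**The concern.** A trapezoid area for one patient needs all five utilities. When one is missing, the analyst must drop the patient, fill the gap, or estimate the area some other way, and the plan does not choose. The simplest course is to keep complete areas only. The ICER denominator would then come from patients who were reached at every contact and were alive at 12 months.

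Two things are at stake. The first is precision, because every observed value from a patient with one gap is discarded. The second is bias, if the reason for missing a contact is related to health and differs by arm. Some difference by arm is plausible. The extra spirometry visits come near the start for intervention patients and near the end for usual care, and the final payment is tied to different events in the two arms (section 4F). A patient who dies also has no complete area. Leaving that patient out removes the loss of QALYs that the analysis should count.

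**Working it through.** The documents state no dropout rate, EQ-5D standard deviation, correlation or expected QALY difference, so there is no figure of the plan's to reproduce. The planned 500 patients, the five time points and the model terms come from the documents. Everything else below is assumed.

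**1. Share with a complete area.** Baseline is taken as observed, and each of four contacts is missed independently with probability m. The share is (1 − m)^4 and the standard error factor is 1/√share.

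| m | Share | Patients of 500 | SE factor |
|---|---|---|---|
| 5% | 0.815 | 407 | 1.11 |
| 10% | 0.656 | 328 | 1.23 |
| 15% | 0.522 | 261 | 1.38 |
| 20% | 0.410 | 205 | 1.56 |

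At m = 10%, the follow-up values kept are 4 × 0.656 = 2.62 of 4 × 0.9 = 3.6 observed per patient, or 73%. About 27% of the collected values are thrown away. If the same patients missed all four contacts, 500 × 0.9 = 450 would be complete, so clustering of misses softens the loss.

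**2. What a repeated-measures likelihood model recovers.** The trapezoid weights are 0.125, 0.25, 0.25, 0.25 and 0.125 years, which sum to 1. With an assumed within-patient correlation of 0.5 to 0.8 (exchangeable or first-order autoregressive) and clustering ignored, the effective number of patients at m = 10% is 486 to 497 for intermittent misses and 430 to 483 for permanent dropout. Complete cases give 328.

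**3. Bias, by simulation.** The set-up is 250 per arm and a utility gain of 0.03 at every follow-up time, so the true QALY difference is 0.03 × (0.25 + 0.25 + 0.25 + 0.125) = 0.026. About 10% miss each contact, more often when the last observed utility was low. The SD is 0.2 and the correlation 0.6, except in the last row (0.25 and 0.7). Odds ratios (OR) of missing are per SD lower utility. Ranges are across repeated runs that differed in how strongly missingness depended on utility.

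| Missingness tracks health in | Complete cases | Observed means, no within-patient covariance | Likelihood with within-patient covariance |
|---|---|---|---|
| both arms alike | 0.020 to 0.024 | not tabulated | 0.026 |
| intervention arm only, mild (OR about 1.6) | 0.050 | 0.030 to 0.040 (all intervention-only runs) | 0.025 |
| intervention arm only, stronger | 0.064 to 0.079 | as above | 0.024 to 0.029 |
| usual care only (OR about 2.7) | −0.051 | 0.006 | 0.025 |

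**4. Scale.** With SD 0.2 and correlation 0.6, the variance of an area is 0.04 × (0.6 + 0.4 × 0.21875) = 0.0275, where 0.21875 is the sum of the squared weights. The standard error of the difference with full data is √(2 × 0.0275/250) = 0.0148. With complete cases at m = 10% it is 0.0148 × 1.23 = 0.018. The bias when arms are alike is at most 0.026 − 0.020 = 0.006, a third of that standard error. In the mild intervention-only case it is 0.050 − 0.026 = 0.024, or 1.3 standard errors. The estimate is then about 0.050/0.026 = 1.9 times the truth, which nearly halves the ICER for the same cost difference.

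The third column of the table matters for the fix. Using every observed value, as a model with only PCP and hospital levels would, removes part of the bias. The within-patient covariance removes most of the rest.

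**The case against.** The strongest reply is that the plan never says complete cases. A reader might infer that it discards every patient with one gap. The documents do not support that: an area built from group means, interpolation or multiple imputation fits the same sentence. This stands. The loss is what happens by default, not what the text prescribes.

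A reader might also infer that the Aim 2 model, simply applied to the EQ-5D, would solve the problem. It would not. As written it names no patient level, and its quality-of-life outcome is not tied to EQ-5D utility. In one intervention-only run it corresponds to an estimate of 0.036 against 0.026, leaving about 40% of the true effect as bias.

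The magnitudes are assumed. Independent misses overstate the loss if the same patients miss repeatedly, and nothing in the documents shows health-related missingness in one arm. The plan also has measures to retain patients: reminder postcards, an in-person option, $20 for each interim contact, $95 at the end, and emergency contacts. These lower the likely miss rate but do not say what happens when a contact is missed.

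On deaths, section 6 speaks of risk and gives no rate. A reader might infer that an arm with more deaths will be flattered. That is the direction of the error if decedents are dropped, but the plan does not say they are, no size can be given, and the simulations contain no deaths. Finally, this is an economic analysis that uses a secondary outcome, so the primary outcomes are untouched.

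**Conclusion.** The point holds as a weakness of the Aim 3 estimator: it has no model and no handling of missed contacts or deaths, and its default reading is inefficient and open to bias. It does not hold as a claim that the plan has chosen complete cases, or that the trial's QALY result will be biased.

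The size depends on inputs that the documents do not give. Under independent misses of 5 to 20% per contact, between 407 and 205 of 500 patients would have a complete area. Bias is small if missingness is alike in both arms. If it tracks health in one arm only, it can double the QALY difference or more, or reverse its sign, depending on the arm. The change should be made before the Aim 3 data are analysed; it is not a reason to alter the conduct of the trial.

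**What to change.** In the Cost-Effectiveness paragraph of Aim 3, define the incremental QALY as the sum, with weights 0.125, 0.25, 0.25, 0.25 and 0.125, of the arm differences in mean EQ-5D utility at months 0, 3, 6, 9 and 12. Take the means from the mixed model of Aim 2, fitted to EQ-5D utility on its own scale so that the weights apply directly. Add a within-patient covariance, or a patient random effect, to the PCP and hospital levels.

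Count utility as 0 from the date of death, so that a decedent's later values are known zeros and the model does not carry utilities past death.

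Refit the model in each bootstrap sample. Resample PCPs, because they are the randomised unit, and keep each patient's cost and QALY data together.

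No new data are needed beyond dates of death. The cost is a few sentences in the plan and extra programming, since the model is refitted in every bootstrap sample. The estimate then relies on missingness being at random given the observed EQ-5D values. That is a weaker assumption than complete cases need, but still untestable.
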